### 3 Study design

Figure 3-1 Study Overview

\* Day 2 visit only needed for site participating in the BAT laboratory assessment

This is a Phase 2 multi-center, randomized, participant- and investigator- blinded, placebo controlled study to assess the safety and clinical efficacy of four dosing regimens of oral remibrutinib versus placebo (CCI for one month (4-5 weeks); CCI for one month (4-5 weeks); CCI for one month (4-5 weeks); placebo for 3 weeks followed by remibrutinib CCI for 1-2 weeks; and placebo for one month (4-5 weeks) in adult participants with a medically confirmed diagnosis of IgE-mediated peanut allergy. Approximately 72 participants will be randomized in this study to one of the five arms (randomization ratio of 2:2:2:1:1). Participants initially assigned to the 3-week placebo arm will receive the first dose of blinded remibrutinib treatment at the Day 22 visit. CCI

The study will include the following:

- 1. Screening period (duration of 4 weeks with 3 required visits):** Written informed consent will be obtained before any study-related assessments or procedures are performed. Consented participants will be assessed for study eligibility during the Screening Visit 1 and will need to meet all eligibility criteria for this visit in order to progress to Screening Visits 2 and 3 (DBPCFC parts 1A and 1B), conduct of the double-blind, placebo-controlled food challenge.

To minimize bias in reaction for individual participants, sequence in which allergen or placebo material is provided will be determined by IRT. Participants who receive placebo-allergen challenge material during DBPCFC part 1A will receive peanut-allergen challenge material during DBPCFC part 1B; while those who receive peanut-allergen challenge material during DBPCFC part 1A will receive placebo-allergen challenge material during DBPCFC part 1B. The participant and all study staff, except the unblinded pharmacist/staff member who will re-constitute the allergen, will be blinded to which visit administers which (allergen or placebo).

Those participants who meet threshold requirements for allergen challenge (as described in [Section 5.1](#)) will proceed to the treatment randomization visit and study treatment period.

To ensure participants meet inclusion/exclusion criteria for exposure to both peanut-allergen and placebo-allergen, unblinding of the food challenge will be disclosed a minimum of 30 minutes following the maximum dose of DBPCFC part 1B at screening visit 3.

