2. **Treatment period:** The treatment period is approximately one month long and can range from 4-5 weeks due to the visit windows allowed as well as due to the need to collect end-of-treatment data across 3 visits that have required minimum spacing between them.

Study participants will be seen in the clinic on Day 1 (treatment randomization), Day 8, and Day 22, for on-treatment clinic visits and drug dispensation. Study participants will also be seen in the clinic for three end-of-treatment visits, which collect primary and secondary one month endpoint data, collectively. These will occur on Day 25, Day 26 (DBPCFC part 2A) and Day 28 (DBPCFC part 2B).

The study treatment will begin on Day 1 at the randomization visit and will continue until the CCI of the DBPCFC part 2B end-of-treatment visit. The study treatment is three placebo -matched tablets administered by the participant at home CCI

Participants will continue study drug dosing CCI from Day 1 visit through the CCI dose of their Day 28 (DBPCFC part 2B) visit. The CCI administration of study drug on Day 28 (DBPCFC part 2B) will be the last dose.

There is a minimum of 2 days (48 hours) needed between the DBPCFC parts 1 and 2. Given the need for flexibility to accommodate holidays and weekends, participants will have a window of plus 2 days for all three end-of-treatment visits on Days 25, 26 and 28, which, if maximized, may extend treatment to up to 34 days. Treatment will not exceed 34 days. Participants will be encouraged to try to maintain the visit schedule as written and avoid utilizing windows as much as possible to keep the study treatment period as short as possible.

3. **End of Study Visit and Follow Up Period:** After completion of Day 28 (DBPCFC part 2B) visit, participants will return to clinic 3 days post-last-dose on Day 31 for the end of study visit, which will include post-dose assessments and study evaluations including safety, pharmacokinetics, post-treatment biomarkers, etc. (See [Table 8-1](#)). The end-of-study visit should not be earlier than 3 days (72 hours) after the last dose of study drug to facilitate proper PD/biomarker analysis. Additionally, a 30-day post-last-dose safety call will be placed to the participant and will complete participation in the study.

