### 6.1.3 Treatment arms/group

Participants will be assigned at the visit on Day 1 for study treatment randomization to one of the following five treatment arms to achieve a ratio of 2:2:2:1:1 at the end of the study. Each participant will begin taking the prescribed regimen consisting of two placebo and one active tablet OR three placebo tablets CCI starting on Day 1 (randomization) and continuing until Part 2B DBPCFC end-of-treatment visit. The CCI dose on the day of Part 2B DBPCFC end-of-treatment visit will be the last dose administered. The CCI dose will not be administered.

1. Remibrutinib CCI every day on Days 1 through 28
2. Remibrutinib CCI every day on Days 1 through 28
3. Remibrutinib CCI every day on Days 1 through 28
4. Placebo CCI every day on Days 1 through 28
5. Placebo CCI every day for Days 1-21, followed by remibrutinib CCI every day on Days 22 through 28

Treatment duration is approximately one month (4-5 weeks). Participants will receive study drug from the site staff at randomization (Day 1), Day 8 and Day 22 visits. Dispensation of study drug by the site to the participants must be recorded. Participants will administer drug at home, except on clinic days. On clinic days, participants should withhold their CCI dose and take it at the instructed time during the visit (based on assessment schedule and PK draws, etc.). If participant has already taken the dose CCI, this should be noted on patient diary and eCRF. If visit includes PK assessments, participant should be rescheduled to the next available clinic day for the PK visit. Participants' compliance with taking study drug must be

recorded in the source documents and the corresponding electronic Case Report Form (eCRF) to document administration. Dosing information may be collected in eCRF for specific visits (e.g.: visits with PK draws). Study drug reconciliation should be performed at each study visit or per the monitoring plan. The follow-up period is a non-treatment period of 30 days after the last dose of study drug during which neither study treatment will be administered nor study assessments will be performed.

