## 2.1.1 General definitions

### 2.1.1.1 Study treatment

In this document, 'study medication', 'study treatment' or 'study drug' will be used to refer to investigational therapy assigned to a participant. Study drug refers to either remibrutinib or placebo.

The treatment arms in this study are as follows.

- Remibrutinib CCI
- Remibrutinib CCI
- Remibrutinib CCI
- Placebo for 3 weeks followed by remibrutinib CCI for 1 week
- Placebo

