## 2.7 Safety analyses

For all safety analyses, the safety set will be used. All listings will be presented by treatment group and tables will be presented by treatment arm and overall. For the 3 weeks Placebo followed by remibrutinib CCI for 1 week arm, the AEs will be listed by the placebo period and remibrutinib period separately to differentiate the AEs that occurred during the respective period.

Safety summaries (tables, figures) will include only data from the on-treatment period with the exception of baseline data from Screening Visits 1, 2 and 3 which will also be summarized where appropriate (e.g. change from screening summaries). In addition, a separate summary for death including on treatment and post treatment deaths will be provided. In particular, summary tables for AEs will summarize only on-treatment events, with a start date during the on-treatment period.

The on-treatment period lasts from the date of first administration of study treatment (Day 1) to 28 days after the end of treatment.

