### 2.7.1 Adverse events (AEs)

All AEs summarized will be displayed by treatment group and overall. All AEs listings will be presented by treatment arm and participant.

All events that the investigator classifies as reactions associated to the DBPCFC or SPT must be captured on the designated eCRF and will not be reported on the AE eCRF. These events will be reported separately and not included in reporting of treatment-emergent AEs (events started after the first dose of study medication or events present prior to start of treatment but increased in severity based on preferred term).

The number (and percentage) of participants with treatment emergent AEs will be summarized in the following ways:

1. by treatment, primary system organ class and preferred term
2. by treatment, primary system organ class, preferred term and maximum severity
3. by treatment, Standardized MedDRA Query (SMQ) and preferred term

Separate summaries will be provided for study medication related AEs, death, serious adverse events (SAEs), and other significant AEs leading to discontinuation. In case of sparse events in any of these categories occur, only a listing will be provided if deemed adequate.

A participant with multiple AEs within a primary system organ class is only counted once towards the total of the primary system organ class.

For the legal requirements of clinicaltrials.gov, two required tables on treatment-emergent AEs which are not SAEs with an incidence greater than a certain threshold based on the final database and on treatment-emergent SAEs and SAEs suspected to be related to study treatment will be provided by system organ class and PT on the safety set population.

If for a same patient, several consecutive AEs (irrespective of study treatment causality, seriousness and severity) occurred with the same SOC and PT:

- a. a single occurrence will be counted if there is  $\leq 1$  day gap between the end date of the preceding AE and the start date of the consecutive AE
- b. more than one occurrence will be counted if there is  $> 1$  day gap between the end date of the preceding AE and the start date of the consecutive AE

For occurrence, the presence of at least one SAE / SAE suspected to be related to study treatment / non SAE has to be checked in a block e.g., among AE's in a  $\leq 1$  day gap block, if at least one SAE is occurring, then one occurrence is calculated for that SAE.

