### 2.7.3 Laboratory data

All laboratory data will be listed by treatment group, participant, and visit/time and, if normal ranges are available, abnormalities will be flagged. The summary of laboratory evaluations will be presented for three groups of laboratory tests (Hematology, Serum chemistry and Urinalysis).

Summary statistics will be provided by visit/time for treatment group, and overall. Shift tables using the low/normal/high/(low and high) classification will be used to compare baseline to the worst on-treatment value.

The laboratory parameters in Table 2-3 will be analyzed with respect to numerical Common Terminology Criteria for Adverse Event (CTCAE) grades (according to the most recent version)

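### For the delayed-start arm, AE tables and worst-value or any-time laboratory tables pool 21 placebo days with the remibrutinib days; only the AE listing is split

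*SAP*

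**What the plan says.** - **Regimen.** Protocol section 6.1.3 defines the arm as "Placebo CCI every day for Days 1-21, followed by remibrutinib CCI every day on Days 22 through 28". Section 3 confirms that these participants "will receive the first dose of blinded remibrutinib treatment at the Day 22 visit". Visit windows can lengthen treatment ("which, if maximized, may extend treatment to up to 34 days"), which adds remibrutinib days in this arm.
- **Window.** SAP section 2.7 sets one on-treatment period for all arms: "The on-treatment period lasts from the date of first administration of study treatment (Day 1) to 28 days after the end of treatment". SAP section 2.1.1.1 states "Study drug refers to either remibrutinib or placebo", so the Day 1 placebo dose opens the window. Treatment-emergent status (section 2.7.1) and baseline (section 2.1.1.3) are tied to the same first dose.
- **AE outputs.** SAP section 2.7.1: "All AEs summarized will be displayed by treatment group and overall". For the delayed-start arm, section 2.7 adds that "the AEs will be listed by the placebo period and remibrutinib period separately". The sentences before it treat listings and tables as different outputs, so as written the split covers listings only.
- **Laboratory outputs.** SAP section 2.7.3 gives summary statistics by visit. It also gives shift tables that "will be used to compare baseline to the worst on-treatment value", CTCAE abnormalities both per visit window and at any post-baseline time, newly occurring liver abnormalities, and renal alerts at any post-baseline point. No period split is stated for any of these.

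**The concern.** In the 4-week arms, every event in the window follows the first remibrutinib dose. In the delayed-start arm, only events from Day 22 do. An AE, or the worst laboratory value, from Days 1-21 enters the same column as events on drug, and the table cannot show which came first. The SAP recognises the need to tell the periods apart, since it asks for this in the listing, but a listing gives no incidence, no period denominator and no comparison between arms.

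Safety and tolerability of multiple doses is a secondary objective, and this is the only arm in which participants switch from placebo to drug. If the first week or two on drug raises AE rates, the pooled column will show less of it than it could.

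**Working it through.** **Arm size.** Protocol section 12.8 gives 72 participants at 2:2:2:1:1, so this arm has 72 x 1/8 = 9. With about 10% discontinuation, 9 x 0.90 = 8.1, in line with the stated 7 to 8 completers. The safety set counts everyone dosed, so 9 is used below.

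**Window shares.** There are 21 placebo days and 7 nominal remibrutinib days, or 34 - 21 = 13 if visit windows are used in full. The SAP adds 28 days after end of treatment.

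| Window | Placebo share | Remibrutinib dosing share |
|---|---|---|
| SAP, nominal (28 + 28 = 56 days) | 21/56 = 37.5% | 7/56 = 12.5% |
| SAP, maximum (34 + 28 = 62 days) | 21/62 = 33.9% | 13/62 = 21.0% |
| Dosing days, nominal (28) | 21/28 = 75% | 7/28 = 25% |
| Dosing days, maximum (34) | 21/34 = 61.8% | 13/34 = 38.2% |

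**Dilution.** Assume a constant background hazard that doubles on remibrutinib dosing days only. The cumulative hazard ratio against placebo over the SAP window is then:
- delayed-start arm: (21 + 7 x 2 + 28)/56 = 63/56 = 1.125;
- 4-week arms: (28 x 2 + 28)/56 = 84/56 = 1.5.

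If the effect lasted through the 28-day follow-up, the values would be (21 + 35 x 2)/56 = 1.625 and 2.0. Over dosing days alone (the window in protocol section 12.5.2, which the SAP has replaced) they would be (21 + 14)/28 = 1.25 and 2.0.

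**Participants entering from placebo time.** The documents give no expected AE rate for this population, so the background is assumed: 20% per 28 days, range 10% to 40%. The 21-day incidence is 1 - (1 - p)^(21/28). At 20% it is 0.154, or 1.4 of 9 participants. At 10% the count is 0.7 and at 40% it is 2.9.

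**No drug effect.** At 20% background, both the delayed-start and the placebo arm have expected incidence 1 - 0.8^(56/28) = 36.0% over the SAP window. The pooled window creates no excess over placebo.

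**What a split gains.** Same assumptions: 20% background, hazard doubled on dosing days only.
- Whole SAP window: 1 - 0.8^(63/28) = 39.5% against 36.0%, risk ratio 1.10.
- From first remibrutinib dose (7 + 28 = 35 days), with placebo cut at the same point: 1 - 0.8^(42/28) = 28.4% against 1 - 0.8^(35/28) = 24.3%, risk ratio 1.17.
- At 10% background the ratio moves from 1.11 to 1.18; at 40%, from 1.07 to 1.13.
- Over dosing days only, at 20%, it moves from 1.22 (24.3% against 20.0%) to 1.95 (10.6% against 5.4%).

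**The case against.** The strongest reply has five parts.

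1. *The information is already reported.* With 9 participants, a listing by period shows each AE with its phase, and SAP section 2.7.1 allows listings in place of tables when events are sparse. This is fair for AEs, but the listing still gives no incidence or comparator and does not cover laboratory data.
2. *Several outputs already separate the phases.* Laboratory statistics, vital signs and ECG summaries are by visit. The scheduled on-treatment ECGs fall on Day 8 (placebo in this arm) and Day 25 (remibrutinib). This stands, and these outputs are outside the point.
3. *There is no false harm signal.* A reader might infer that placebo events are tabulated as harms of a one-week remibrutinib regimen. The documents do not support that: the arm's label names the placebo weeks as well as the remibrutinib week, and the placebo arm is counted over the same window.
4. *The dilution is modest on the SAP's own window.* A reader might also infer that placebo-time events make up most of the column, or that a doubled hazard shows as 1.25 against 2.0. Both use the 28 dosing days. On the SAP's 56-day window the placebo share is 37.5%, and the 28-day follow-up dilutes as well.
5. *Splitting only this arm would harm comparability.* A column from Day 22 beside whole-window columns has no concurrent comparator, and the late period contains the challenge days (Days 26 and 28), so a constant hazard is doubtful. This stands and shapes the fix: the placebo arm needs the same cut, and the whole-arm tables should remain the main display.

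**Conclusion.** The point holds as a gap in presentation. For the delayed-start arm, AE tables, worst-on-treatment laboratory shifts and any-time post-baseline laboratory tables combine 21 days before any remibrutinib with the time after it, and only the AE listing tells them apart. The consequence is dilution toward no difference, not a spurious excess.

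On the SAP window, the size is 1.125 against 1.5 for a hazard doubled on dosing days only. Splitting would move the illustrative risk ratio from 1.10 to 1.17. With about 9 participants, a difference of that size could not be told from chance, so the gain is clearer attribution rather than power. The window shares follow directly from the documents; the background AE rates, the constant hazard and the doubling are assumptions.

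**What to change.** In SAP sections 2.7, 2.7.1 and 2.7.3:

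- Keep the whole-arm tables as the randomised comparison.
- Add supplementary AE tables, and supplementary worst-value and any-time laboratory tables, with the delayed-start arm split at the first remibrutinib dose. The second period ends where the SAP window ends.
- Use as the remibrutinib-period denominator the participants who took at least one remibrutinib dose. Count an AE in that period only if it starts or worsens after that dose.
- Use as that period's laboratory baseline the last value before the first remibrutinib dose. The laboratory rows of the assessment schedule are not legible in the text available, so a Day 22 pre-dose sample could not be confirmed; this definition works either way.
- Cut the placebo arm at Day 22 in the same tables, by the same rules, so that the remibrutinib period has a concurrent comparator over the same study days.
- Give exposure-adjusted rates beside percentages, because the periods differ in length.

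The cost is SAP wording and table shells. The period flag is already needed for the AE listing, so the extra programming is small, and trial conduct does not change. The downside is more columns, each with about 9 participants or fewer.

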### 2.7.1 Adverse events (AEs)

All AEs summarized will be displayed by treatment group and overall. All AEs listings will be presented by treatment arm and participant.

All events that the investigator classifies as reactions associated to the DBPCFC or SPT must be captured on the designated eCRF and will not be reported on the AE eCRF. These events will be reported separately and not included in reporting of treatment-emergent AEs (events started after the first dose of study medication or events present prior to start of treatment but increased in severity based on preferred term).

The number (and percentage) of participants with treatment emergent AEs will be summarized in the following ways:

1. by treatment, primary system organ class and preferred term
2. by treatment, primary system organ class, preferred term and maximum severity
3. by treatment, Standardized MedDRA Query (SMQ) and preferred term

Separate summaries will be provided for study medication related AEs, death, serious adverse events (SAEs), and other significant AEs leading to discontinuation. In case of sparse events in any of these categories occur, only a listing will be provided if deemed adequate.

A participant with multiple AEs within a primary system organ class is only counted once towards the total of the primary system organ class.

For the legal requirements of clinicaltrials.gov, two required tables on treatment-emergent AEs which are not SAEs with an incidence greater than a certain threshold based on the final database and on treatment-emergent SAEs and SAEs suspected to be related to study treatment will be provided by system organ class and PT on the safety set population.

If for a same patient, several consecutive AEs (irrespective of study treatment causality, seriousness and severity) occurred with the same SOC and PT:

- a. a single occurrence will be counted if there is  $\leq 1$  day gap between the end date of the preceding AE and the start date of the consecutive AE
- b. more than one occurrence will be counted if there is  $> 1$  day gap between the end date of the preceding AE and the start date of the consecutive AE

For occurrence, the presence of at least one SAE / SAE suspected to be related to study treatment / non SAE has to be checked in a block e.g., among AE's in a  $\leq 1$  day gap block, if at least one SAE is occurring, then one occurrence is calculated for that SAE.

The number of deaths resulting from SAEs suspected to be related to study treatment and SAEs irrespective of study treatment relationship will be provided by SOC and PT.

#### **2.7.1.1 Adverse events of special interest / grouping of AEs**

AEs of special interest (AESI) are defined in the latest version of the compound electronic Case Retrieval Strategy (eCRS). The classification reflects the safety topics of interest identified in the current version of the remibrutinib Development Safety Profiling Plan, and may be updated based on review of accumulating data. The number and percentage of participants with treatment emergent AEs of special interest will be summarized by risk category, PT and treatment.

The Compound Case Retrieval Strategy (CRS) will be used to determine the MedDRA search criteria to be used to identify events of special interest. The most recent list of adverse events

of special interest at the time of database lock will be used. CCI

- CCI
- CCI
- CCI

### 2.7.2 Deaths

All deaths in the clinical database that occur during the treatment period will be listed.

### 2.7.3 Laboratory data

All laboratory data will be listed by treatment group, participant, and visit/time and, if normal ranges are available, abnormalities will be flagged. The summary of laboratory evaluations will be presented for three groups of laboratory tests (Hematology, Serum chemistry and Urinalysis).

Summary statistics will be provided by visit/time for treatment group, and overall. Shift tables using the low/normal/high/(low and high) classification will be used to compare baseline to the worst on-treatment value.

The laboratory parameters in Table 2-3 will be analyzed with respect to numerical Common Terminology Criteria for Adverse Event (CTCAE) grades (according to the most recent version)

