**Table 8-4 Laboratory Assessments**

Test Category	Test Name
Hematology	Hematocrit, Hemoglobin, [in the case of clinically significant anemia the following parameters will be assessed: Erythrocyte Mean Corpuscular Hemoglobin (MCH), Erythrocyte Mean Corpuscular Hemoglobin Concentration (MCHC), Erythrocyte Mean Corpuscular Volume (MCV)], Platelets, Erythrocytes, Leukocytes, and Differential (Basophils, Eosinophils, Lymphocytes, Monocytes, Neutrophils, Bands)
Chemistry	Albumin, Alkaline phosphatase (ALP), Alanine Aminotransferase (ALT), Aspartate Aminotransferase (AST), Gamma-glutamyl transferase (GGT), Lactate dehydrogenase (LDH), Calcium, Magnesium, Phosphate, Chloride, Sodium, Potassium, Creatinine, Creatine Kinase (CK), Direct Bilirubin, Indirect Bilirubin (in case of clinically significant elevation), Total Bilirubin, Total Cholesterol, Low Density Lipoprotein (LDL) Cholesterol, High-Density Lipoprotein (HDL) Cholesterol, Total Protein, Triglycerides, Urea Nitrogen or Urea, Uric Acid, Amylase, Lipase, C-reactive protein (CRP), estimated Glomerular Filtration Rate (eGFR), Glucose (either fasting or non-fasting).
Coagulation	Prothrombin time (PT), International normalized ratio (INR), Activated partial thromboplastin time (APTT)
Hepatitis markers	Hepatitis B screening: Antibodies against hepatitis B core antigen (HBcAb); antibodies against hepatitis B surface antigen (HBsAb); hepatitis B surface antigen (HBsAg, only in participants who are positive for HBcAb), and hepatitis B-Deoxyribonucleic acid (HBV-DNA, only in participants who are positive for HBcAb). Hepatitis C screening: hepatitis C virus antibodies (anti-HCVAb) and hepatitis C-Ribonucleic acid (HCV-RNA, only in participants who are positive for anti-HCVAb)
Hepatitis B re-activation monitoring	Only in participants who are positive for HBcAb and negative for HBsAg and HBV-DNA at screening: HBsAg, HBV-DNA
HIV testing	HIV test performed at screening
Additional tests	Immunoglobulins (total IgE, IgG, IgA, IgM) Follicle-stimulating hormone (FSH) (for female participants with unclear fertility status)
Pregnancy Test	Serum / Urine pregnancy test for women of childbearing potential (refer to 'Pregnancy and assessments of fertility' Section 8.4.3 )

Test Category	Test Name

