#### 8.4.4 Appropriateness of safety measurements

The selected safety monitoring assessments (including laboratory assessments covering clinical chemistry, hematology, coagulation status and immunoglobulins, as well as clinical and physical assessments, triplicate ECG monitoring and general AE assessments) are reliable and well-established standard measures which allow valid and close safety monitoring of the trial's patient population, with regards to their disease, to the compound they are treated with, remibrutinib, and also to their overall medical safety.

In addition to safety assessments that are standard in this population, participants are not eligible to join the study if they have a history of a severe or life-threatening hypersensitivity event needing an ICU admission or intubation within 60 days prior to Screening Visit 1 or uncontrolled asthma at Screening Visit 1. Spirometry is performed in asthmatic participants before each DBPCFC for safety purposes.

Also, study treatment will be discontinued if the participant experiences a life-threatening hypersensitivity event needing an ICU admission or intubation OR a serious hypersensitivity event suspected to be related to study treatment.

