### 12.5.2.3 Clinical laboratory evaluations

All laboratory data will be listed by treatment group, participant, and visit/time and, if normal ranges are available, abnormalities will be flagged. Summary statistics will be provided by visit/time for treatment group, and overall. Shift tables using the low/normal/high/(low and high) classification will be used to compare baseline to the worst on-treatment value.

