### **16.1.2 Guidance on immunizations**

Administration of live or live-attenuated vaccines (including live or live-attenuated SARS-CoV-2 (COVID-19)) should be avoided 6 weeks before and during treatment with remibrutinib and for 4 weeks after the last study drug dose. Further, participants are encouraged to perform necessary last dose of **non-live** vaccines (including for COVID-19) at least 4 weeks before randomization, if available, and according to local practice.

The safety of and ability to generate a primary or anamnestic response to immunization with live, live-attenuated, or inactivated vaccines during remibrutinib treatment has not been investigated. The response to vaccination (including non-live vaccines) could be impaired when B-cells are inhibited.

It is recommended that the Investigator review the participant's immunization history as part of the initial screening procedure for a participant being considered for treatment with remibrutinib.

Vaccination of the participant (including COVID-19 vaccine), in compliance with local area vaccination guidelines for the patient population being treated, is recommended prior to administration of remibrutinib.

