
Objective(s)	Endpoint(s)

To evaluate the safety and tolerability of multiple doses of remibrutinib

To assess the ability of remibrutinib to impact skin mast cells through the assessment of allergen-specific skin prick test (SPT)

To assess the pharmacokinetics (PK) of remibrutinib

	

Treatment-emergent adverse events, vital signs, ECG, and laboratory values, including immunoglobulin levels

Change from screening in SPT mean wheal diameters at one month

Remibrutinib concentrations in blood and PK parameters (including, but not necessarily limited to: Cmax, AUClast, AUCtau, Tmax)

Exploratory objective(s)	Endpoint(s) for exploratory objective(s)
CCI	

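### SAP 2.7.3 restricts laboratory summaries to three test groups, leaving the immunoglobulins, part of a named secondary safety endpoint, with no on-treatment summary by arm

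*SAP*

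**What the plan says.** The secondary safety endpoint, worded alike in protocol Table 2-1 and SAP Table 1-1, is "Treatment-emergent adverse events, vital signs, ECG, and laboratory values, including immunoglobulin levels". No other laboratory class is singled out in it.

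Protocol Table 8-4 collects "Immunoglobulins (total IgE, IgG, IgA, IgM") under a heading for additional tests. It collects "Prothrombin time (PT), International normalized ratio (INR), Activated partial thromboplastin time (APTT") under a separate coagulation heading. Protocol 8.4.4 describes the safety monitoring as including "laboratory assessments covering clinical chemistry, hematology, coagulation status and immunoglobulins", so all four are treated as distinct domains.

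On analysis, protocol 12.5.2.3 states "Summary statistics will be provided by visit/time for treatment group, and overall", and adds shift tables from baseline to the worst on-treatment value. It does not restrict these by test group. SAP 2.7.3 keeps both provisions but puts a new sentence before them: "The summary of laboratory evaluations will be presented for three groups of laboratory tests (Hematology, Serum chemistry and Urinalysis"). It also states "All laboratory data will be listed by treatment group, participant, and visit/time", with abnormal values flagged where normal ranges exist. SAP Section 4 reports no change to the protocol's analyses.

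**The concern.** The SAP adds a restriction that the protocol lacks, and the restriction leaves out the one laboratory class that the endpoint names. A programmer working from SAP 2.7.3 would produce tables for haematology, chemistry and urinalysis, and only a listing for immunoglobulins.

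At stake is whether the report answers its own secondary endpoint. At 2:2:2:1:1, 72 randomised participants give 72 × 2/8 = 18 in each one-month remibrutinib arm and 72 × 1/8 = 9 in each of the other two. Comparing arms of that size over several visits from a participant listing is impractical, above all for a shift within the normal range, where no flag appears. The plan does have a reason to look. Protocol 4.5 discusses infection risk through BTK's role in B cells and other immune cells, and protocol 16.1.2 says "The response to vaccination (including non-live vaccines) could be impaired when B-cells are inhibited". The latter concerns vaccine response and not immunoglobulin concentration, so it supports interest in the measurement and predicts nothing about it.

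**Working it through.** No sample size, power or error rate bears on this point. The check compares the tests collected with the tests that the SAP says will be summarised.

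**Step 1. Tests collected (protocol Table 8-4).** Four immunoglobulins: total IgE, IgG, IgA, IgM. Three coagulation tests: PT, INR, APTT. Neither set is filed under haematology, chemistry or urinalysis.

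**Step 2. Where the SAP could summarise them.**

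| SAP location | Immunoglobulins | Coagulation |
|---|---|---|
| 2.3.2 baseline characteristics | Total IgE, baseline only | none |
| 2.6.1 secondary endpoints | Peanut-specific IgE and IgG4 only, a different endpoint | none |
| 2.7.3 three-group summary | not named | not named |
| Table 2-3 (CTCAE grades) | none | INR |
| Table 2-4 (liver criteria) | none | INR, combined with ALT or AST |
| Table 2-5 (renal criteria) | none | none |
| Table 5-1 (worst-case direction) | none | none of PT, INR, APTT |

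**Step 3. Count.**
- Immunoglobulins with a specified post-baseline summary by arm: 0 of 4. With a baseline summary by arm: 1 of 4 (total IgE).
- Coagulation tests entering any by-arm summary: 1 of 3 (INR). PT and APTT enter none.

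**Step 4. Could another document cover the gap?** SAP Section 1 says that all objectives are covered, apart from certain exploratory biomarker outputs sent to a separate plan. A secondary safety endpoint is not exploratory, so that exception does not reach it. SAP 2.10 is redacted and cannot be checked; it follows the PK and PD sections and precedes the interim analysis, where exploratory analyses would be expected.

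**Step 5. Is the narrowing declared?** Section 4 says there is none. Elsewhere the SAP annotates its departures: the analysis-set conflict in 2.2, the supplementary estimands not run in 2.5.5, and the dropped maximum-tolerated-dose analyses in 2.6.1. There is no such note in 2.7.3.

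**The case against.** The strongest reply is that the wording is loose and not exclusionary. The sentence promising summary statistics by visit and arm is carried into SAP 2.7.3 and can be read as covering all laboratory data. The SAP also uses chemistry broadly: INR appears in the chemistry part of Table 2-3 and fibrinogen under chemistry in Table 5-1, so coagulation may be meant to fall there. Tables 2-3 and 5-1 are not inventories of what is summarised; urinalysis is expressly summarised yet appears in neither. This has force for coagulation and weakens any argument from absence in those tables. It does less for immunoglobulins, which no SAP laboratory table mentions and which the protocol files elsewhere. If full coverage is intended, the restricting sentence still needs correction.

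Several stronger readings might be inferred, and the documents do not support them:

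- *That immunoglobulins are never summarised.* Total IgE is summarised by arm at baseline.
- *That the data are lost, or that only abnormal values are shown.* All values are listed and flags are additional. Under protocol 10.1.2, clinically significant abnormal results count as adverse events, which are summarised by arm.
- *That a fall in immunoglobulins would be missed.* Neither document gives data predicting a fall over at most 34 days of treatment.
- *That omitting PT and APTT hides the bleeding risk.* Protocol 4.5 places that risk in platelet activation, and states that BTK inhibition does not affect plasmatic coagulation. Platelets are summarised.
- *That the sponsor chose to drop the endpoint.* SAP Table 1-1 retains it, which fits an oversight better.

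**Conclusion.** The point holds for immunoglobulins. Followed as written, SAP 2.7.3 gives IgG, IgA, IgM and post-baseline total IgE a listing by participant and no on-treatment summary by arm, although they are named within a secondary safety endpoint and the protocol's summary provision is not so restricted. This goes beyond missing detail, because a stated rule produces the gap. For PT and APTT it is a minor clarification: coagulation is not named in the endpoint, and its place within the SAP's chemistry group is ambiguous.

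This is a reporting gap worth closing, with no effect on the primary analysis. The conclusion assumes that the three-group sentence governs the summary sentence that follows it, that redacted text (SAP 2.10 and the adverse events of special interest) does not supply the summaries, and that the Table 8-4 panel is measured after baseline. Part of the visit schedule in protocol Table 8-1 could not be read, so the sampling visits for IgG, IgA and IgM were not confirmed.

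**What to change.** In SAP 2.7.3, add immunoglobulins (total IgE, IgG, IgA, IgM) as a summary group. Present value and change from baseline by visit and arm, with a shift table where normal ranges exist. Add the four tests to Table 5-1, each with a stated direction of interest.

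As a minor addition, make coagulation (PT, INR, APTT) a summary group too. The reason is that protocol Table 8-4 and Section 8.4.4 treat it as its own safety category; the change need not rest on the bleeding mechanism.

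If the sponsor does intend the narrower scope, SAP Section 4 should record and justify it as a departure from protocol 12.5.2.3.

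The cost is an SAP wording change and a few standard tables from data already planned for collection. Trial conduct and the primary analysis do not change.
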